oxide/prostacycline, use of selective fiberoptic insufflation, hypotension unresponsive to fluids and/or vasoactive drugs, new arrhythmias unresponsive to intervention, need for high dosage of vasoactive drugs, need for massive transfusion, life-threatening surgical complication (including major bleeding, tension pneumothorax and intracranial injury), hypoxemia and hypercapnia rescue maneuvers; 4) postoperative extrapulmonary complications, including systemic inflammatory response syndrome, sepsis, severe sepsis, septic shock, extrapulmonary infection, coma, acute myocardial infarction, acute renal failure, disseminated intravascular coagulation, stroke, hepatic failure, and gastrointestinal failure; 5) need for unexpected intensive care unit admission or readmission; 6) any postoperative respiratory intervention used for respiratory failure (new requirement of non-invasive ventilation or mechanical ventilation); 7) number of hospital-free days at day 28; 8) in-hospital mortality; 9) 90-day mortality; 10) arterial blood gas analysis during surgery (PaO₂, PaCO₂, pH_a). All definitions are available in **Table 1**.

Cleaning and closing of the database

The database will be locked as soon as all data are entered and all discrepant or missing data are resolved, after all efforts are employed to fix missing data, complete the database, and we consider that the remaining issues cannot be fixed. At this step, the data will be reviewed before database locking. After locking, the data will be exported for statistical analysis. At this stage, permission for access to the database will be removed for all investigators, and the database is archived.

Missing data

No or minimal losses to follow-up for the primary outcome is anticipated. Complete-case analysis will be carried out for all outcomes. However, if more than 5% of missing data is found for the primary outcome, a sensitivity analysis using multiple imputations and estimating-equation methods will be carried out. Multiple imputation will consider imputation models based on prognostic baseline and post-baseline variables under a missing at random assumption.

Sample size

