models with binomial distribution and an identity link for binary variables (reported as difference in percentages). Plots comparing ventilatory variables and vital signs among the groups during the first three hours of surgery and in the last hour will be drawn (presenting the data as mean and 95% confidence interval in each time point).

Other daily characteristics

Daily variables will be reported according to the description in **Proposed Inserts**. Absolute differences between groups will be calculated using median regression for continuous variables (reported as median difference) and generalized linear models with binomial distribution and an identity link for binary variables (reported as difference in percentages). Plots comparing daily variables among the groups will be constructed (presenting the data as mean and 95% confidence interval in each time point).

Primary outcome

The effect of 'higher PEEP' compared to 'lower PEEP' on the incidence of PPC will be assessed using a mixed-effect generalized linear model with binomial distribution and identity link, with sites included as random effects to account for the clustering effect and reported as absolute difference with a two-sided 95% confidence interval. Results will be presented in a table of outcomes (**Proposed Inserts**).

Secondary outcomes

For binary outcomes, the effect of 'higher PEEP' compared to 'lower PEEP' will be assessed using a mixed-effect generalized linear model with binomial distribution and identity link, with sites included as random effects to account for the clustering effect and reported as absolute difference with a two-sided 95%

confidence interval. For continuous outcomes, the comparison will be made using a mixed-effect median regression with sites also including as clustering effect, and reported as median difference with a two-sided 95% confidence interval. 90-day mortality will be assessed using Kaplan–Meier curves, and hazard ratios with 95% confidence intervals will be calculated with (shared-frailty) Cox proportional hazard models without adjustment for covariates and including sites as frailty. The proportional hazard assumptions will be tested using scaled Schoenfeld residuals and alternative parametric survival models will be used if the proportionality assumption is not sustained. In addition, a Holm–Bonferroni correction to control the family-wide error rate to the p values for all secondary outcomes will be done and presented in a Table.

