Figure 2	Postoperative Pulmonary Complications in Prespecified Subgroups A forest plot showing the absolute difference and two-sided 95% confidence intervals with p value for interaction calculated via a test for treatment-by-subgroup interaction in the regression model. A solid line of reference in the number 1 and a dashed line of reference in the overall effect will be shown.
Online Supplement	
eTable 1	Rate of Missing Data A table showing the rate of missing data.
eTable 2	Additional Baseline Characteristics A table showing additional baseline characteristics.
eTable 3	Additional Intraoperative Characteristics A table showing additional intraoperative characteristics.
eTable 4	Intraoperative Fluid and Drug Therapy A table reporting intraoperative fluid and drug therapy each arm.
eTable 5	Protocol Deviations A table describing protocol deviations.
eTable 6	Daily Assessment of Included Patients A table describing daily assessment of patients.
eTable 7	Additional Daily Assessment of Included Patients A table describing daily assessment of patients.
eTable 8	Daily Signs and Laboratory of Included Patients A table describing daily assessment of patients.
eTable 9	Day 1 Fluid and Drug Therapy A table reporting day 1 fluid and drug therapy each arm.
eTable 10	Multiplicity adjustment for secondary outcome analyses A table showing the observed p values for all the secondary outcomes and ordered from the lower until the higher and the corrected p values using a Holm-Bonferroni correction
eTable 11	Sensitivity Analyses for the Primary Outcome A table showing the proposed sensitivity analyses for the primary outcome (count analysis, common effect test, average relative effect test and heterogeneity of treatment effect)
eFigure 1	Tidal Volume, PEEP, Peak Pressure, Plateau Pressure, Driving Pressure and FiO ₂ During Surgery Line graph reporting the mean and 95% confidence interval of the variables at induction, final positioning with two lung ventilation, 10 minutes of one lung ventilation and at the end of surgery by treatment group.
eFigure 2	VAS Dyspnea, VAS Thoracic Pain, VAS Coughing Pain, Respiratory Rate, SpO ₂ and Mean Arterial Pressure During the First Five Days of Follow-Up Line graph reporting the mean and 95% confidence interval of the variables in the first five days of follow-up by treatment group.

eFigure 3

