eTable 6 – Daily Assessment of Included Patients

	Higher PEEP (n = XXX)	Lower PEEP (n = XXX)	Absolute Difference (95% CI)	p value
Day 1				
Still in hospital – no. (%)				
Unplanned ICU admission – no. (%)				
New requirement of NIV or IMV – no. (%)				
New requirement of NIV – no. (%)				
Indication – no. (%)				
Standard of care				
Respiratory failure				
Other				
Type – no. (%)				
CPAP				
NPPV				
Other				
Pressure level, cmH ₂ O				
Duration, hours				
New requirement of IMV – no. (%)				
Indication – no. (%)				
Resurgery				
Respiratory failure				
Other				
Duration, hours				
Physiotherapy – no. (%)				
Breathing exercises – no. (%)				
Incentive spirometry – no. (%)				
Cumulated ambulation score				
Day 2				
Still in hospital – no. (%)				
Unplanned ICU admission – no. (%)				
New requirement of NIV or IMV – no. (%)				
New requirement of NIV – no. (%)				
Indication – no. (%)				
Standard of care				
Respiratory failure				
Other				
Type – no. (%)				
CPAP				
NPPV				
Other				
Pressure level, cmH ₂ O				
Duration, hours				
New requirement of IMV – no. (%)				
Indication – no. (%)				
Resurgery				

eTable 6 – Daily Assessment of Included Patients

	Higher PEEP (n = XXX)	Lower PEEP (n = XXX)	Absolute Difference (95% CI)	p value
Respiratory failure				
Other				
Duration, hours				
Physiotherapy – no. (%)				
Breathing exercises – no. (%)				
Incentive spirometry – no. (%)				
Cumulated ambulation score				
Day 3				
Still in hospital – no. (%)				
Unplanned ICU admission – no. (%)				
New requirement of NIV or IMV – no. (%)				
New requirement of NIV – no. (%)				
Indication – no. (%)				
Standard of care				
Respiratory failure				
Other				
Type – no. (%)				
CPAP				
NPPV				
Other				
Pressure level, cmH ₂ O				
Duration, hours				
New requirement of IMV – no. (%)				
Indication – no. (%)				
Resurgery				
Respiratory failure				
Other				
Duration, hours				
Physiotherapy – no. (%)				
Breathing exercises – no. (%)				
Incentive spirometry – no. (%)				
Cumulated ambulation score				
Day 4				
Still in hospital – no. (%)				
Unplanned ICU admission – no. (%)				
New requirement of NIV or IMV – no. (%)				
New requirement of NIV – no. (%)				
Indication – no. (%)				
Standard of care				
Respiratory failure				
Other				
Type – no. (%)				
CPAP				

eTable 6 – Daily Assessment of Included Patients

	Higher PEEP (n = XXX)	Lower PEEP (n = XXX)	Absolute Difference (95% CI)	p value
NPPV				
Other				
Pressure level, cmH ₂ O				

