	Higher PEEP (n = XXX)	Lower PEEP (n = XXX)	Absolute Difference (95% CI)	p value
Airway secretion – no. (%)				
Purulent/yellow color				
Not purulent				
VAS dyspnea				
VAS thoracic pain				
VAS coughing pain				
Day 4				
Impairment of wound healing – no. (%)				
Superficial				
Deep				
Surgical wound infection – no. (%)				
Superficial				
Deep				
Antibiotics – no. (%)				
Therapeutically				
PONV – no. (%)				
Return of bowel function – no. (%)				
Airway secretion – no. (%)				
Purulent/yellow color				
Not purulent				
VAS dyspnea				
VAS thoracic pain				
VAS coughing pain				
Day 5				
Impairment of wound healing – no. (%)				
Superficial				
Deep				
Surgical wound infection – no. (%)				
Superficial				
Deep				
Antibiotics – no. (%)				
Therapeutically				
PONV – no. (%)				
Return of bowel function – no. (%)				
Airway secretion – no. (%)				
Purulent/yellow color				
Not purulent				
VAS dyspnea				
VAS thoracic pain				
VAS coughing pain				

Data are median (quartile 25th - quartile 75th) or N / total (%).

Abbreviations: PEEP is positive end-expiratory pressure; PONV is postoperative nausea and vomiting; VAS is visual analogue scale.

eTable 8 – Daily Signs and Laboratory of Included Patients

	Higher PEEP (n = XXX)	Lower PEEP (n = XXX)	Absolute Difference (95% CI)	p value
Day 1				
Respiratory rate, breaths/min				
Heart rate, bpm				
Mean arterial pressure, mmHg				
Temperature, °C				
Tympanic				
Nasal/oral				
Bladder				
Other				
SpO ₂ , %				
FiO ₂ , %				
Hemoglobin, g/dL				
Creatinine, mg/dL				
Blood urea nitrogen, mg/dL				
ALT, U				
AST, U				
Bilirubin, mg/dL				
INR				
C-reactive protein, g/L				
Day 2				
Respiratory rate, breaths/min				
Heart rate, bpm				
Mean arterial pressure, mmHg				
Temperature, °C				
Tympanic				
Nasal/oral				
Bladder				
Other				
SpO ₂ , %				
FiO ₂ , %				
Hemoglobin, g/dL				
Creatinine, mg/dL				
Blood urea nitrogen, mg/dL				
ALT, U				
AST, U				
Bilirubin, mg/dL				
INR				
C-reactive protein, g/L				
Day 3				
Respiratory rate, breaths/min				
Heart rate, bpm				
Mean arterial pressure, mmHg				
Temperature, °C				
Tympanic				
Nasal/oral				

eTable 8 – Daily Signs and Laboratory of Included Patients

	Higher PEEP (n = XXX)	Lower PEEP (n = XXX)	Absolute Difference (95% CI)	p value
Bladder				
Other				
SpO ₂ , %				
FiO ₂ , %				
Hemoglobin, g/dL				
Creatinine, mg/dL				
Blood urea nitrogen, mg/dL				
ALT, U				
AST, U				
Bilirubin, mg/dL				
INR				
C-reactive protein, g/L				

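### Later-day bedside readings, and NIV/IMV details on any day, are compared between arms with CIs and p values although they probably exist only for patients still admitted or ventilated (minor; supplementary tables only)

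*SAP*

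**What the plan says.** The section 'Other daily characteristics' sets the analysis: "Absolute differences between groups will be calculated using median regression for continuous variables (reported as median difference"), with a binomial model and identity link for binary variables. It adds: "Plots comparing daily variables among the groups will be constructed (presenting the data as mean and 95% confidence interval in each time point").

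The shells follow this. eTables 6, 7 and 8 each have the columns "Absolute Difference (95% CI") and p value, over blocks for days 1 to 5. One of them is headed "eTable 8 – Daily Signs and Laboratory of Included Patients", with one n per arm in the column heads. In Table 3 (list of proposed tables and figures), eFigure 2 is described as: "Line graph reporting the mean and 95% confidence interval of the variables in the first five days of follow-up by treatment group". It covers three VAS scores, respiratory rate, SpO₂ and mean arterial pressure.

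Three other places bear on the point.

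- Every daily block of eTable 6 opens with the row "Still in hospital – no". (%), so the plan expects discharges between days 1 and 5.
- 'Outcomes' lists "number of hospital-free days at day 28" as a secondary outcome, so time in hospital is treated as something the intervention may change.
- 'Missing data' says: "Complete-case analysis will be carried out for all outcomes". It gives no rule for a daily reading absent because the patient has gone home or died.

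Nowhere are the later-day comparisons called descriptive or conditional on being in hospital.

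**The concern.** Randomisation protects a comparison of everyone randomised. It does not protect a comparison among patients selected by something that happened afterwards. Being in hospital on day 4 is such a selection, and so is having received NIV. If one arm sends its uncomplicated patients home earlier, those left in that arm are on average sicker. A difference in C-reactive protein, SpO₂ or dyspnea score could then appear although the ventilation strategy had no effect on that variable. A CI and p value beside the row invite a causal reading, and the reader cannot separate a treatment effect from selective discharge.

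The second group of rows does not depend on discharge at all. NIV pressure level, NIV duration and IMV duration exist only for patients who received that support, so even the day-1 comparison is within a post-randomisation subset.

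At stake is the reading of supplementary tables and one supplementary figure. The primary outcome, the secondary outcomes and the subgroup analyses do not use these rows.

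**Working it through.** **Which rows are affected.** The SAP gives no data-collection rule, so the rows have to be sorted by their nature.

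- Probably read only in hospital: all of eTable 8 (vital signs, temperature, laboratory values) and the VAS scores in eTable 7.
- Exist only in ventilated patients, on any day: NIV pressure level, NIV duration and IMV duration in eTable 6.
- Can be defined for every randomised patient: still in hospital; also new NIV, new IMV and unplanned ICU admission, if a discharged patient counts as not having the event.

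**Inputs.** The SAP attaches no figure to the daily variables. From 'Sample size' and Table 2 (Z-statistic boundaries): PPC 23% versus 17.25%, and N = 2259 before dropout. 2259/0.95 = 2377.9, which reproduces 2378, or 1189 per arm. Discharge rates and severity effects below are assumptions.

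**Simulation.** 1189 per arm, 2000 trials per scenario. Severity U is standard normal. The daily variable is U plus independent standard normal error (SD √2 ≈ 1.41), with no effect of arm or of PPC. The log-odds of PPC rise by 1 per unit of U, with intercepts giving about 23% or 17%. The log-odds of staying in hospital on days 2, 3, 4 and 5 are 3.0, 1.2, 0.4 and −0.3, plus U, plus 2 if the patient has a PPC. Medians are compared among those still in hospital at two-sided 5%. The true difference is zero throughout.

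- (a) No arm effect on PPC or discharge.
- (b) Arm acts on discharge only through the planned PPC effect.
- (c) As (b), and the higher-PEEP arm has 0.5 lower log-odds of staying each day.

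| Day | (a) rejection | (b) median difference; rejection | (c) in hospital, higher vs lower PEEP | (c) median difference; rejection |
|---|---|---|---|---|
| 2 | 5.8% | 0.002; 5.0% | 90.2% vs 93.7% | 0.032; 6.6% |
| 3 | 6.0% | 0.006; 5.2% | 62.7% vs 72.7% | 0.094; 20.2% |
| 4 | 5.0% | 0.017; 5.4% | 39.1% vs 51.1% | 0.141; 28.6% |
| 5 | 5.2% | 0.032; 6.2% | 23.2% vs 33.9% | 0.166; 27.2% |

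The largest spurious difference, 0.166, is 0.166/1.41 ≈ 0.12 SD of the variable.

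**A milder selection, by formula.** Suppose PPC is 23% in both arms, 95% of PPC patients are in hospital on day 5, and uncomplicated patients are in hospital in 50% versus 40%. The share with a PPC among those in hospital is:

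- 0.23×0.95 / (0.23×0.95 + 0.77×0.50) = 0.2185/0.6035 = 36.2%
- 0.23×0.95 / (0.23×0.95 + 0.77×0.40) = 0.2185/0.5265 = 41.5%

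The gap is 5.3 points, but it concerns PPC share, which is not a row of eTables 6 to 8. If PPC status is the only link to a row, the row's spurious difference is 0.053 times the gap between PPC and non-PPC patients. With 2259/2 ≈ 1130 per arm, and row values assumed:

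- binary row 30% versus 10%: 0.053×20 ≈ 1.1 points, significant in about 8% of trials
- binary row 50% versus 20%: 0.053×30 ≈ 1.6 points, about 9%
- continuous row, gap 0.5 SD: 0.053×0.5 ≈ 0.026 SD, about 7%
- continuous row, gap 0.8 SD: 0.053×0.8 ≈ 0.042 SD, about 11%

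With 50% versus 45%, these four fall to about 5.5–6%.

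**The case against.** The strongest reply is that the premise is not in the document. The SAP never says that readings stop at discharge; the protocol and case report form may settle it, and they are not at hand. The complete-case sentence speaks of outcomes, and most of these rows are not listed outcomes. This stands, so the point is conditional for bedside rows and does not extend to rows where discharged patients can be counted. It does not help the NIV and IMV pressure and duration rows.

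Second, part of the remedy is already in the plan. Unexpected ICU admission and respiratory intervention for respiratory failure are secondary outcomes 5 and 6, planned by intention to treat with Holm–Bonferroni correction. The footnotes promise N / total for binary rows, and the still-in-hospital row will expose unequal discharge. This also stands. The footnote does not cover continuous rows, however. The rule in 'Baseline characteristics' that a denominator is stated when values are missing is not repeated for the daily tables.

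Third, a reader might infer more than the SAP supports:

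- *That these tables carry a false-positive rate near one half.* The 5.3-point gap above would be significant in about 49% of trials, but only for in-hospital PPC share, which none of the three tables reports.
- *That a true benefit would show up as harm because PPC prolong stay.* Scenario (b) tests that path and finds 5–6%. With uncomplicated patients discharged equally (50% in hospital), the formula gives 36.2% PPC for lower PEEP and 0.1725×0.95 / (0.1725×0.95 + 0.8275×0.50) = 28.4% for higher PEEP, which favours higher PEEP. A reversal needs comparable patients to be discharged at different rates by arm, and nothing in the SAP suggests that.
- *That every later-day row is affected.* The shells hold 21 + 16 + 18 = 55 rows per day, or 220 over days 2 to 5, but these include the still-in-hospital row and event rows that can be defined for everyone.

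**Conclusion.** The point holds in a limited form, with minor severity. The SAP plans a difference, CI and p value for daily rows without fixing who is in the denominator. For readings taken only in hospital, the later-day comparisons have no randomised interpretation. For NIV pressure level and NIV and IMV duration this is so on every day.

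Whether a bias results depends on two conditions: discharge of comparable patients differs by arm, and staying in hospital is related to the variable. Under the planned PPC effect alone the distortion was negligible (5–6% rejection). Under an assumed direct arm effect on discharge it reached 20–29% on days 3 to 5. Both results rest on assumed discharge and severity parameters. The SAP supplies none, so they show what can happen and do not predict what will.

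**What to change.** In 'Other daily characteristics' and the shells of eTables 6 to 8:

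- For days 2 to 5, rows measured only in hospital: show arm summaries with the number assessed per arm and day, and remove the difference and p value.
- On all days, rows that exist only in patients given NIV or IMV: do the same. Keeping day-1 p values for these would not make them randomised comparisons.
- Keep differences and p values for rows defined for all randomised patients: still in hospital, and new NIV, new IMV and unplanned ICU admission if computed over all randomised patients. State that denominator, and refer to secondary outcomes 5 and 6 for the all-patient comparison.
- Label eFigure 2 as showing patients in hospital.

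This changes wording and shells only and needs no new data. The cost is fewer p values in the supplement.

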Time-to-event analyses for PPC	Kaplan–Meier curves will be used to report time to postoperative pulmonary complications, and hazard ratios with a 95% confidence interval will be calculated with Cox proportional hazard models without adjustment for covariates.	No time-to-event analysis planned to be performed for PPC.
Time-to-event analyses for 90-day mortality	Hazard ratios with 95% confidence intervals will be calculated with Cox proportional hazard models without adjustment for covariates and including sites as frailty.	Hazard ratios with 95% confidence intervals will be calculated with (shared-frailty) Cox proportional hazard models without adjustment for covariates and including sites as frailty.
Subgroup analysis (definition)	---	Added two additional subgroups: body mass index and duration of one-lung ventilation.
Subgroup analysis (method)	The effects on subgroups will be evaluated according to the interaction effects between each subgroup and the study arms by generalized linear models and presented in a forest plot.	Analyses of heterogeneity of effects across subgroups will be performed with the use of treatment-by-subgroup term added to the primary model and will be presented in a forest plot.

LIST OF PROPOSED INSERTS

Table 1 – Baseline Characteristics of the Included Patients

	Higher PEEP (n =)	Lower PEEP (n =)
Age, years		
Age ≥ 65 years – no. (%)		
Female gender – no. (%)		
Body mass index, kg/m ²		
Body mass index ≥ 30 kg/m ²		
ARISCAT score		
ARISCAT ≥ 45 – no. (%)		
ASA physical status– no. (%)		
1		
2		
3		
4		
Priority of surgery – no. (%)		
Elective		
Urgent		
Emergency		
Surgical procedure – no. (%)		
Thoracoscopic		
Open		
Converted from thoracoscopic to open		
Cumulated ambulation score		
Co-existing disorders – no. (%)		
Hypertension		
Heart failure		
Coronary artery disease		
Diabetes		
Obstructive sleep apnea		
Chronic obstructive pulmonary disease		
Use of noninvasive ventilation		
Active cancer		
Respiratory infection within last month		
Smoking status		
Never		
Former (cessation > 3 months)		
Current		
Alcohol (> 2 drinks/day)		
Preoperative signs		
SpO ₂ , %		
Respiratory rate, breaths/min		
Heart rate, beats per minute		
Mean arterial blood pressure, mmHg		

Data are median (quartile 25th - quartile 75th) or N / total (%).

Abbreviations: PEEP is positive end-expiratory pressure; ARISCAT is The Assess Respiratory Risk in Surgical Patients in Catalonia; ASA is American Society of Anesthesiology; SpO₂ is pulse oximetry.

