Able to perform function independently		
Transfer from sitting-to-standing-to-sitting (from armchair) – no. (%)		
Unable to perform function despite assistance from 2 people		
Only able to perform function with assistance from 1 or 2 people		
Able to perform function independently		
Walking (with appropriate walking aid) – no. (%)		
Unable to perform function despite assistance from 2 people		
Only able to perform function with assistance from 1 or 2 people		
Able to perform function independently		
≥ 4 metabolic equivalents		
Co-existing disorders		
Heart failure – no. (%)		
NYHA score		
1		
2		
3		
4		
Coronary artery disease – no. (%)		
CCS score		
Atrial flutter / fibrillation – no. (%)		
Acute		
Paroxysmal		
Chronic		
Diabetes – no. (%)		
Dietary		
Oral medication		
Insulin		
Obstructive sleep apnea – no. (%)		
Apnea/Hypopnea Index (events / hour)		
STOP BANG Score		
Chronic obstructive pulmonary disease – no. (%)		
Steroids use		
Inhalation therapy		
Use of noninvasive ventilation		
Continuous positive airway pressure		
Intensity of support (pressure level, cmH ₂ O)		

eTable 2 – Additional Baseline Characteristics

	Higher PEEP (n =)	Lower PEEP (n =)
Duration (hours / day)		
Gastroesophageal reflux – no. (%)		
≥ 1 event/day		
≥ 1 event/week		
≥ 1 event/month		
Respiratory infection within last month – no. (%)		
Lower respiratory infection		
Medications – no. (%)		
Use of antibiotics (last 3 months)		
Use of statins		
Use of aspirin		
Preoperative signs		
FiO ₂ , %		
Temperature, °C		
Tympanic – no. (%)		
Nasal/oral – no. (%)		
Bladder – no. (%)		
Other		
Preoperative laboratory tests		
Blood gas obtained – no. (%)		
Arterial – no. (%)		
pH		
PaO ₂ , mmHg		
PaCO ₂ , mmHg		
Hemoglobin, g/dL		
INR		
Creatinine, mg/dL		
BUN, mg/dL		
ALT, U		
AST, U		
Bilirubin, mg/dL		
C-reactive protein, mg/L		
Airway secretion – no. (%)		
VAS dyspnea		
VAS thoracic rest pain		
VAS coughing pain		
Spirometry obtained – no. (%)		
Forced vital capacity, L		
Predicted postoperative forced vital capacity, %		
Forced expiratory volume at 1 second, L/1 sec		

eTable 2 – Additional Baseline Characteristics

	Higher PEEP (n =)	Lower PEEP (n =)
Predicted postoperative forced expiratory volume at 1 second, %		
Forced expiratory volume at 1 second / Forced vital capacity, %		
Total lung capacity, L		
Diffusing capacity for carbon monoxide		
mmol/min/kPa		
ml/min/mmHg		
Predicted postoperative diffusing capacity for carbon monoxide, %		

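### Daily vital-sign, laboratory and VAS comparisons, and the intraoperative blood gases, are modelled without the preoperative value that the trial collects: a modest loss of precision that is cheap to recover

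*SAP*

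**What the plan says.** Under Secondary outcomes, the SAP fixes one model for every continuous secondary outcome: "For continuous outcomes, the comparison will be made using a mixed-effect median regression with sites also including as clustering effect". Item 10 of the secondary outcomes is "10) arterial blood gas analysis during surgery (PaO₂, PaCO₂, pH_a"), so the three gas variables fall under that model, with site as the only term besides treatment.

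Under Other daily characteristics the rule is "Absolute differences between groups will be calculated using median regression for continuous variables (reported as median difference"). Neither a baseline covariate nor a site term is named there. The shells "eTable 8 – Daily Signs and Laboratory of Included Patients" and eTable 7 have columns for absolute difference, 95% confidence interval and p value for days 1 to 5, so these comparisons are inferential.

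Preoperative counterparts are collected:
- Table 1, under "Preoperative signs": SpO2, respiratory rate, heart rate and mean arterial pressure.
- eTable 2: FiO2, temperature and the VAS scores for dyspnea, thoracic pain and coughing pain.
- eTable 2, under "Preoperative laboratory tests": hemoglobin, INR, creatinine, BUN, ALT, AST, bilirubin and C-reactive protein, and also pH, PaO2 and PaCO2.

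The gas values sit below the row "Blood gas obtained – no". (%), followed by a separate count of arterial samples. The Missing data section prescribes complete-case analysis for all outcomes and gives no rule for a missing covariate.

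**The concern.** A patient's creatinine, hemoglobin, heart rate or pain score after surgery usually resembles the value before it. If the earlier value is left out of the model, that known variation between patients stays in the residual, and the interval for the treatment difference is wider than the collected data allow. Every vital sign and laboratory test in eTable 8 and all three VAS scores in eTable 7 have a preoperative counterpart, so the point applies to both tables. It also applies in principle to secondary outcome 10, a named secondary outcome inside the Holm-Bonferroni family. What is at stake is interval width and power for these comparisons, not their validity.

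**Working it through.** **The plan's own figures.** The SAP gives no standard deviation, correlation, power or coverage for any of these variables, so there is no figure on this point to reproduce. Its sample size (2259, and 2259/0.95 = 2378 after 5% dropout) concerns the binary primary outcome and does not bear on it.

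**Assumed inputs.** ρ is the correlation between preoperative and later value (0.3, 0.5, 0.7). s is the share of patients with a preoperative value (1 or 0.5). Unadjusted power is 80% at two-sided 0.05, so the standardised effect is 1.960 + 0.842 = 2.802.

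**Formulas.** Each SE ratio compares the adjusted analysis with the unadjusted analysis of all patients.
- Baseline complete: √(1 − ρ²).
- Baseline in share s, patients without it dropped: √((1 − ρ²)/s). This is below 1 only if s > 1 − ρ².
- Baseline in share s, gap filled with a constant plus an indicator: about √(1 − sρ²), never above 1.
- Power after adjustment: Φ(2.802/SE ratio − 1.960).

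| ρ | SE ratio, s = 1 | Power, s = 1 | SE ratio, s = 0.5, dropped | SE ratio, s = 0.5, indicator | Power, s = 0.5, indicator |
|---|---|---|---|---|---|
| 0.3 | 0.954 | 83.6% | 1.349 | 0.977 | 81.8% |
| 0.5 | 0.866 | 89.9% | 1.225 | 0.935 | 85.0% |
| 0.7 | 0.714 | 97.5% | 1.010 | 0.869 | 89.7% |

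Example at ρ = 0.5:
- Complete baseline: √0.75 = 0.866, and Φ(2.802/0.866 − 1.960) = Φ(1.276) = 0.899.
- Half dropped: √(0.75/0.5) = 1.225.
- Half filled with an indicator: √(1 − 0.125) = 0.935, and Φ(2.802/0.935 − 1.960) = Φ(1.036) = 0.850.

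**Does the formula suit median regression?** The variance factor comes from the linear model for means. Simulated median regressions with normal data and complete baselines gave SE ratios of 0.94, 0.86 and 0.74 at ρ = 0.3, 0.5 and 0.7, close to 0.954, 0.866 and 0.714.

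**Coverage other than one half.** If patients without a baseline are dropped, the SE ratios at ρ = 0.3, 0.5 and 0.7 are 1.140, 1.035 and 0.854 for s = 0.7, and 1.006, 0.913 and 0.753 for s = 0.9. Plain adjustment can therefore lose precision even at fairly high coverage.

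**Absolute scale.** Take about 1130 patients per arm (2259/2) and normal data. The SE of a difference in medians is √(π/2) × √(2/1130) = 1.2533 × 0.0421 = 0.0527 SD. The difference detectable with 80% power is 2.802 × 0.0527 = 0.148 SD unadjusted, and 0.866 × 0.148 = 0.128 SD adjusted at ρ = 0.5.

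**Holm, for outcome 10 only.** If the family has 10 tests, the first step is 0.05/10 = 0.005, where 80% power becomes 84.6%, 92.0% and 98.9% at ρ = 0.3, 0.5 and 0.7 with complete baselines. The family size is itself an assumption. Outcome 10 contains three variables; counted separately they give 9 + 3 = 12 tests and a first step of 0.0042.

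**The case against.** The strongest case against is that nothing here is an error. Randomisation makes the comparison valid without a baseline term, the plan is consistently unadjusted apart from site (90-day mortality is explicitly so), and a simple analysis is a legitimate choice. The stake is also small, as the move from about 0.15 to 0.13 SD shows. All of this stands, and it is why the point ranks only as an improvement.

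Three further objections limit the point:
- **Blood gases.** A reader might infer that precision on outcome 10 is certainly being thrown away. The SAP does not support that. Its shell allows for patients with no preoperative gas or a non-arterial one, the share is not given, and under the complete-case rule plain adjustment could widen the interval. The preoperative FiO2 may also differ from that during surgery, which would lower ρ for PaO2. The SAP does not give the timing of the intraoperative gases; the protocol may.
- **Holm.** A reader might also infer that the multiplicity correction makes the loss on the daily variables worse. It does not: the correction covers the secondary outcomes, and the daily variables are not among the ten listed.
- **Estimand.** With a covariate, median regression estimates a conditional median difference. Unless treatment simply shifts the distribution, this need not equal the difference between the two group medians printed beside it. The wording has to say so.

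These objections narrow the point but do not remove it. The indicator approach drops no patient. Randomisation takes place immediately before surgery, so whether a preoperative value is missing should not depend on the assigned arm. The unadjusted medians can stay in the tables.

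**Conclusion.** The point holds as a matter of efficiency only. Omitting the preoperative value introduces no bias and does not touch the primary outcome. For the daily variables, if baselines are nearly complete, adjustment would narrow intervals by about 5%, 13% or 29% at ρ = 0.3, 0.5 or 0.7. For PaO2, PaCO2 and pH the gain is uncertain and may be small: from 80% to about 82% to 85% power at half coverage and ρ between 0.3 and 0.5, and only if patients without a preoperative gas are kept in the model.

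The correlations, the coverage and the 80% starting power are all assumptions, since the SAP gives none of them. The daily variables are supportive and lie outside the ten secondary outcomes. It is a cheap improvement, not a flaw in the plan's validity.

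**What to change.** 1. **Daily variables.** Under Other daily characteristics, state that each continuous variable in eTables 7 and 8 with a preoperative value is analysed by median regression with that value as a covariate. Fill a missing baseline with a constant and add a missing indicator, so that no patient is dropped.
2. **Blood gases.** Under Secondary outcomes, add the preoperative value of the same gas variable to the models for PaO2, PaCO2 and pH, but only with the same missing-baseline rule. State that a non-arterial preoperative gas counts as missing for this purpose, or how else it is used.
3. **Reporting.** Label the adjusted result a conditional median difference and keep the unadjusted group medians beside it.
4. **Holm family.** State how many tests outcome 10 contributes.

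The cost is a few sentences and one covariate plus an indicator per model, with no new data. The SAP is dated January 17, 2024, before the planned end of enrolment, so the change could have been prespecified then. It should be made before database lock; if it comes later, the adjusted results should be labelled post hoc.
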